Study Title: Alteration of Stool Microbiota in Preterm Infants Less than 32 Weeks with Anemia, and Following Blood Transfusion

Date Approved by IRB: November 22, 2017

The University of Texas Southwestern Medical Center at Dallas
Institutional Review Board

Study Title:

Alteration of Stool Microbiota in Preterm Infants Less than 32 Weeks with Anemia, and Following Blood Transfusion

Investigators:

[name]

[name] (PI)

Type of Funding:

Institutional

Purpose:

- To determine if the stool microbiota in preterm infants is altered with anemia.
- To determine if the stool microbiota in preterm infants is altered after blood transfusion.

Background:

Neonatal gut microbiota begins developing at approximately 2 weeks of age and is less diverse than the microbiota of a term infant. Four bacterial classes make up more than 90% of the microbes present in the neonate: *Bacilli*, *Gammaproteobacteria*, *Clostridia*, and *Negativicutes*. There are multiple factors that influence the neonatal gut microbiota, including mode of infant delivery, type of feeds (i.e. formula or breast milk), medications such as antibiotics, and exposure to pathogens in a hospital environment.

Dysbiosis occurs when there is an imbalance in the proportion of bacterial pathogens and commensal bacteria. This can cause a shift away from homeostasis and lead to an inflammatory state and disease. Studies utilizing molecular methods suggest that dysbiosis occurs in neonates with necrotizing enterocolitis (NEC). While results vary, large studies and meta-analyses suggest a predominance of *Gammaproteobacteria* with NEC and a decrease in *Firmicutes* with NEC. There may also be a decrease in bacterial diversity prior to NEC onset.

The relationship between transfusion and necrotizing enterocolitis has been controversial and frequently studied. Despite this, there is a lack of good quality studies on this topic with conflicted findings and the literature does not currently support a relationship between transfusions and NEC. There have been limited studies on the relationship between anemia and NEC. Some suggest that severe anemia and NEC are associated, however this has not been shown in other studies.

While the evidence seems to support a relationship between a change in microbiota and NEC, there is no clear relationship between anemia or transfusion and NEC. There have been no studies evaluating the relationship between anemia or transfusion and a change in microbiota. That is the primary focus of this study.

Hypothesis:

Anemia will result in alteration of the stool microbiota. Transfusion will return microbiota to baseline. The specific alteration in microbiota with anemia may include: increase in *Proteobacteria*, decrease in *Firmicutes*, and/or decrease in microbiota diversity.

Primary Outcome:

- Change in microbiota with anemia

Secondary Outcome:

- Change in microbiota after transfusion

Inclusion Criteria:

- Preterm infants less than 32 weeks gestation at birth
- ≥ 7 days and <30 days on enrollment
- On minimum 100mL/kg enteral feeds

Exclusion Criteria:

- NEC prior to enrollment
- Prior surgery
- Major congenital anomalies
- Oxygen requirement with $\text{FiO}_2 > 50\%$

Methods:**Definitions:**

- Severe anemia will be defined as a hematocrit $< 25\%$.
- Anemia will be defined as a hematocrit ≥ 25 and $<30\%$.
- No anemia will be defined as a hematocrit $\geq 30\%$.

Hematocrit will be tested per patient's care team. In this unit, hematocrit is usually obtained every Monday, and sometimes more frequently.

Sample Collection:

- Collect stool samples weekly (Sunday, Monday, or Tuesday)
- Collect stool samples 1, 4, and 7 days post-transfusion
- Stool will continue to be collected until infants are 38 weeks corrected gestational age (CGA) or discharge (whichever is earlier).

Data Collection:

Hematocrit	Gestational Age
Birthweight	Apgars
Sex	Race
Singleton/Multiple	Age at stool collection and at hematocrit blood sampling
Iron supplementation	Type of feeds (breastmilk/formula feed)
Calorie fortification of feeds	Total days on antibiotics
Number of transfusions	Positive cultures
NEC	Indomethacin exposure

Groups:

Paired samples will be obtained from the same infants, one before and one after onset of anemia. Therefore, the patients will serve as their own controls.

Sample Analysis:

- Stool samples obtained while patient is on antibiotics will not be included in analysis since the microbiota is expected to be significantly changed with large populations wiped out. Stool samples obtained 5 days after completion of antibiotics will be included in analysis again since infants are expected to be recolonized by that time.
- qRT-PCR of samples will be performed to quantify the major bacterial groups: *Proteobacteria*, *Firmicutes*, and *Bacteroides*.
- Next generation sequencing will be done for qualitative analysis and metagenomics profiling of bacteria

Informed Consent:

New admissions to the Parkland NICU will be screened for recruitment if their birth gestational age (OB assigned) is less than 32 weeks 0 days and if they are at least 7 days old.

- If they meet these two criteria, they will be screened to ensure they do not meet exclusion criteria.
- If they do not meet the exclusion criteria, then their feeds will be evaluated. If they are on at least 100mL/kg/day of enteral feeds, then they will be approached for recruitment. Infants that are not yet on 100mL/kg/day of enteral feeds will have their charts assessed daily until 29 days of life. If and when they achieve 100mL/kg/day of enteral feeds, they will be approached for recruitment. If an infant does not achieve 100mL/kg/day of enteral feeds before 30 days of life, they will not be approached for enrollment in this study.
- If an infant meets the above criteria, and once their parent/guardian/LAR provides consent, then stool collection will begin for that infant from the next available defecated diaper. In cases where the patients are not the PI's patients, the study team will inform all the physicians caring for the patients within the NICU about this research study and

once they approve for their patients' (infant's) parents/guardians/LARs to be approached for consenting purpose to enroll the infant into this study, the bedside nurse will check with the parents/guardians/LARs if they would like to be approached. Once they let the beside nurse know if they agree to be approached, the nurse would inform this to [name] (the PI) and [name] (study team) who will be responsible for recruitment of subjects and they would approach the patient's parent/guardian/LAR for consenting purposes.

Sample Size Calculation:

Group sample sizes of 194 achieve 80% power to detect an odds ratio of 1.500 in a design with 2 repeated measurements having a simple covariance structure when the proportion for group 2 is 0.4 and group 1 is 0.5. The alpha level is 0.05.

Statistical Analysis:

Descriptive analysis will use percentages, means, medians, and measures of variability to describe demographic data. Categorical factors will be evaluated using Chi-square or Fisher exact test between the groups. Continuous factors will be evaluated using Student's t-test or Mann-Whitney U test if the data is non-normal distributed between the groups. Repeated measurements will use analysis of variance (ANOVA) to compare groups. The statistical significance level will be 0.05 for all statistical tests.

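### The transfusion outcome names no untransfused comparison, so a before/after change cannot separate a transfusion effect from maturation

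*Protocol*

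**What the plan says.** All references are to the Protocol.

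- **Secondary Outcome:** "Change in microbiota after transfusion", with no comparator named.
- **Hypothesis:** "Transfusion will return microbiota to baseline". This is a causal and directional statement.
- **Methods, Groups:** "Paired samples will be obtained from the same infants, one before and one after onset of anemia", followed by "Therefore, the patients will serve as their own controls". No other grouping or control is defined anywhere.
- **Methods, Sample Collection:** "Collect stool samples 1, 4, and 7 days post-transfusion". Weekly stools are also taken, with no restriction to transfused infants, until 38 weeks corrected age or discharge.
- **Methods, Data Collection:** hematocrit, age at stool and at hematocrit sampling, gestational age, type of feeds and number of transfusions are recorded.
- **Background:** "Neonatal gut microbiota begins developing at approximately 2 weeks of age and is less diverse than the microbiota of a term infant". Feeds, antibiotics and the hospital environment are also listed as influences.
- **Statistical Analysis:** ANOVA is to compare groups for repeated measurements, but no groups are named for the transfusion question.

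**The concern.** A before/after change attributes to transfusion everything that happens between the two stools. That is safe only if the measure would otherwise have stayed still, and the Protocol's own Background says it would not. Infants enter at 7 to 29 days of age and are followed for weeks, through the period in which the microbiota is said to be developing.

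One of the changes hypothesised for anemia is lower diversity, so a return to baseline would be a rise in diversity. If diversity also rises with age, maturation looks exactly like the hypothesised transfusion effect. Recovery from whatever lowered the hematocrit is a second possible route. Moving the pre-transfusion stool closer to the transfusion shortens the interval but does not supply a comparison.

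Transfusion is one of the study's two stated purposes. At stake is whether its hypothesis could be declared supported when transfusion did nothing.

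**Working it through.** **1. The plan's own figure.** The sample size section gives 194 per group for proportions 0.5 and 0.4, two repeated measurements, simple covariance, 80% power and alpha 0.05. The two-sided two-proportion formula, with mean proportion 0.45, gives

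n = [1.96·√(2·0.45·0.55) + 0.8416·√(0.25 + 0.24)]² / 0.10² = 387.3, so 388 observations per group.

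Dividing by 2 uncorrelated measurements gives 194. The figure reproduces. It is not in dispute here, and it contains no transfusion contrast.

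**2. False positives from drift alone, continuous measure.** Assume no transfusion effect, a spontaneous shift of d SDs of the within-infant change, and n transfused infants. The standard error is 1/√n, so

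P(reject) = P(|Z + d√n| > 1.96).

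| n | d = 0.1 | d = 0.2 | d = 0.3 |
|---|---|---|---|
| 40 | d√n = 0.63: 10% | 1.26: 24% | 1.90: 48% |
| 60 | 0.77: 12% | 1.55: 34% | 2.32: 64% |
| 100 | 1.00: 17% | 2.00: 52% | 3.00: 85% |

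The nominal rate is 5%.

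**3. The same check on the plan's binary scale.** Assume a proportion drifts from 0.5 to 0.5 − δ with no transfusion effect, in 194 pairs with within-infant correlation ρ. The variance of the change is v = p₁q₁ + p₂q₂ − 2ρ√(p₁q₁p₂q₂), where q = 1 − p, and the standard error is √(v/194).

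- δ = 0.05: δ/SE = 0.99 (ρ = 0) and 1.40 (ρ = 0.5), so rejection is 17% to 29%.
- δ = 0.10: δ/SE = 1.99 and 2.81, so rejection is 51% to 80%.

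**4. What a comparison costs.** With equal numbers in a transfused and an untransfused series, the standard error of the difference in change is √(2/n), which is √2 times the one-arm value. For a true 0.3 SD effect with 60 per series, 0.3·√60 = 2.32 gives 64% power one-arm, while 0.3·√30 = 1.64 gives 38%. On the binary scale at ρ = 0, a net change of 0.10 at 80% power needs 7.849 × 0.49 / 0.01 = 385 before/after pairs. It needs 7.849 × (0.49 + 0.50) / 0.01 = 778 infants per group for the difference in change.

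**5. Why the intervals must be modelled.** Successive weekly stools are about 7 days apart. The interval from the last pre-transfusion stool to the day-7 stool is at least 7 days. If transfusions fall evenly over the week, it averages 7 + 3.5 = 10.5 days. With an assumed steady drift of 0.2 SD per 7 days, a plain comparison of the two changes leaves 0.2 × 3.5/7 = 0.1 SD of bias. With 100 per series, 0.1·√50 = 0.71 gives 11% rejection instead of 5%. Adjusting for age at each stool addresses this.

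**The case against.** A reader might infer that the Protocol restricts the transfusion analysis to transfused infants. It does not say so. The own-controls sentence follows directly from the anemia pairing, and the ANOVA sentence leaves a transfused/untransfused grouping open. An SAP that is not shown could define one. This stands as a limit: the one-arm contrast is inferred from the outcome wording and from the absence of any other stated control.

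A reader might also infer that the study cannot address its second purpose at all. That goes too far. Whether the microbiota is altered after transfusion is a temporal question, which a before/after change can describe. The causal hypothesis is what needs a comparator.

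Regression to the mean is another tempting explanation, but it is weaker than maturation. Any selection for transfusion would be on hematocrit, so a microbiota measure regresses only as far as it tracks hematocrit or the illness behind it, and that link is what the study is testing.

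Nor do the documents show that enough untransfused anemic weeks exist. No transfusion rule, rate or count is given, and the band below 25% may hold few.

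Finally, a comparison returns the error rate to 5% only if both series share the same drift. Transfusion is not randomised, so confounding by indication would remain. These points limit the remedy and the strength of any claim. They do not make an uncontrolled change able to support a causal statement.

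**Conclusion.** The concern holds in this form: the Protocol pairs a causal hypothesis with an outcome that has no untransfused comparison, in a population whose microbiota it describes as still developing. Followed as written, a change after transfusion would absorb maturation or recovery.

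The size depends wholly on assumed inputs. For shifts of 0.1 to 0.3 SD, the false-positive rate is 10% to 48% with 40 transfused infants and 17% to 85% with 100. The direction and amount of drift, the number transfused and the within-infant correlation are not in the document. These ranges show what drift could do; they do not estimate what it will do.

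This affects a secondary outcome, and a change to the analysis and wording would address it.

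**What to change.** Add to the analysis of the secondary outcome:

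*Each microbiota measure will be analysed in a repeated-measures mixed model using all stools eligible under the antibiotic rule, including weekly stools from infants and weeks without transfusion. The exposure is time since transfusion (none, day 1, day 4, day 7). The model adjusts for postnatal age at each stool, gestational age, most recent hematocrit (for post-transfusion stools, the last value before the transfusion) and type of feeds, with a random infant effect. The adjusted difference from untransfused time will be reported as an association.*

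State also how weekly stools taken more than 7 days after a transfusion are classed. Reword the hypothesis from a causal effect to an association. Report the number of untransfused intervals in each hematocrit band. Where a band has too few, report its before/after change as descriptive only.

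**Cost:** analysis work and a wider interval, with a standard error up to about √2 larger when numbers are equal (the example above falls from 64% to 38% power). Confounding by indication is reduced by adjustment but not removed. No new stools or patients are needed, and nothing changes in who is transfused.

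### The sample re-entry rule makes no exception for NEC arising after enrolment, so NEC between the paired samples can be read as an anemia effect

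*Protocol*

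**What the plan says.** Five statements in the protocol bear on this.

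- **Eligibility.** Exclusion Criteria list "NEC prior to enrollment". NEC after enrolment is not addressed there.
- **Collection.** Under Sample Collection, stool is taken weekly and after transfusions until 38 weeks' corrected age, or discharge if that comes first. No stop at NEC is stated.
- **Sample rule.** Sample Analysis has one sample-level exclusion: "Stool samples obtained while patient is on antibiotics will not be included in analysis". It then ends that exclusion in positive terms: "Stool samples obtained 5 days after completion of antibiotics will be included in analysis again". The reason given is expected recolonisation.
- **NEC and microbiota.** The Background says that results vary, but that large studies and meta-analyses point to predominance of Gammaproteobacteria and a fall in Firmicutes with NEC. It adds: "There may also be a decrease in bacterial diversity prior to NEC onset".
- **Anemia and microbiota.** The Hypothesis reads "The specific alteration in microbiota with anemia may include: increase in" Proteobacteria, with falls in Firmicutes and in diversity as the other possibilities.

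The primary comparison pairs one sample from before the onset of anemia with one from after it, in the same infant. NEC is on the data list, but neither Sample Analysis nor Statistical Analysis says how it is used.

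**The concern.** The features that would signal an anemia effect are those the Background ties to NEC, so the outcome measures cannot tell the two apart. Pairing within infants removes characteristics that stay fixed, but not an event that occurs between the two samples. Infants are free of NEC at enrolment, and the anemic sample is always the later of the pair. NEC that falls between them therefore moves the result in the hypothesised direction. The protocol already treats NEC as disqualifying at entry and already writes a rule on which samples count. Followed literally, that rule puts post-NEC samples back into the primary comparison as ordinary samples. A positive primary result could then be partly NEC dysbiosis.

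**Working it through.** **1. The plan's own figure.** Inputs from Sample Size Calculation: proportions 0.5 and 0.4, odds ratio 1.5, two measurements per infant, simple covariance (read as zero correlation), 80% power, alpha 0.05 (taken as two-sided).

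- Odds ratio: (0.5/0.5)/(0.4/0.6) = 1.50.
- Observations per group: [1.960 × √(2 × 0.45 × 0.55) + 0.842 × √(0.25 + 0.24)]² / 0.10² = 387.3, rounded up to 388.
- Infants per group: 388 × (1 + 0)/2 = 194. Power with 388 observations is 0.801.

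The figure of 194 reproduces and is not in dispute. It supplies the yardstick, a planned difference of 10 points.

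**2. Which NEC episodes matter.**

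| NEC timing | Effect on the pair |
|---|---|
| Before both samples | Both are post-NEC; largely cancels, and could run the other way if recovery is under way |
| Between the samples | Only the after-anemia sample is affected; bias toward the hypothesis |
| After both samples | None |

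Samples taken on antibiotics are already dropped. What remains is NEC-period samples taken off antibiotics, and samples re-admitted from 5 days after the course.

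**3. Possible size.** The protocol gives no NEC incidence, so every input here is an assumption:

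- no true anemia effect;
- 194 pairs;
- a marker positive in p = 0.40 of samples;
- a share f of pairs with NEC between the samples, 2% to 15%;
- a post-NEC sample positive with probability q, 0.7 to 1.0, independently of the earlier sample.

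Spurious shift = f × (q − 0.40).

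False-positive rate: McNemar normal approximation at nominal two-sided 0.05, with within-infant correlation ρ of 0 or 0.5. With d = p(1 − p)(1 − ρ), the discordant probabilities are (1 − f)d + f(1 − p)q (negative to positive) and (1 − f)d + f·p(1 − q) (positive to negative).

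Worked case, f = 0.10, q = 1.0, ρ = 0:

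- d = 0.24; the two probabilities are 0.216 + 0.060 = 0.276 and 0.216; the difference is 0.060 and the sum 0.492.
- Null SE: √(0.492/194) = 0.0504. Alternative SE: √((0.492 − 0.0036)/194) = 0.0502.
- Rejection probability: Φ((0.060 − 1.960 × 0.0504)/0.0502) plus a negligible lower tail = 0.221.

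| f | Shift, q = 0.7 | Shift, q = 1.0 | False-positive rate over both q and both ρ |
|---|---|---|---|
| 2% | 0.006 | 0.012 | 0.052 to 0.063 |
| 5% | 0.015 | 0.030 | 0.060 to 0.130 |
| 10% | 0.030 | 0.060 | 0.092 to 0.355 |
| 15% | 0.045 | 0.090 | 0.145 to 0.639 |

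If the NEC pattern has faded completely by re-entry, q = 0.40 and the shift is zero whatever f is. Leaving out post-NEC samples also sets the shift to zero in this model. It does not remove any fall in diversity that precedes diagnosis.

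**The case against.** **The analysis plan may deal with it.** Handling of later events is often left to a SAP, none is shown here, and NEC is a collected variable. This stands in part: no sentence says that post-NEC samples are kept unadjusted. But the protocol itself fixes which samples count and when they return, and that rule as written has no NEC exception.

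**Persistence is not documented.** The Background describes the microbiota with and before NEC, not after it resolves, and the protocol expects recolonisation by 5 days after antibiotics. This stands, and it is why the size cannot be stated. The recolonisation argument, however, concerns antibiotics and does not address NEC.

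**NEC may be a consequence.** The Background says dysbiosis can lead to disease and places the possible diversity fall before onset. On the link with anemia it says: "Some suggest that severe anemia and NEC are associated, however this has not been shown in other studies". If anemia shifts the microbiota and NEC follows, dropping post-NEC samples removes part of a real effect. This stands, and it is why results with and without those samples are both needed.

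**Stronger readings that a reader might infer, and that the protocol does not support:**

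- That NEC is said to cause the shift. The text reports association only.
- That the study exists to separate anemia from NEC. Its stated focus is anemia or transfusion and the microbiota.
- That post-NEC samples can only fall late, on the anemic side. Enrolment can begin at 7 days, so NEC can precede both samples.
- That surgery after enrolment needs the same treatment. The protocol reports no microbiota shift with surgery.
- That the secondary comparison is biased the same way. Its hypothesis is a return to baseline, so NEC dysbiosis after transfusion would work against it.

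**Conclusion.** The concern holds for NEC arising between the two paired samples. The protocol's re-entry rule admits such samples, its Background links NEC to the pattern hypothesised for anemia, and self-pairing does not protect against it. For those pairs the bias in the primary comparison runs toward the hypothesis.

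The size cannot be established from the protocol. Under the assumptions shown, the shift is 0.6 to 1.2 points at a 2% share, which is negligible, and 3 to 6 points at 10%, which is material against the planned 10. The 9-point extreme needs a 15% share and every post-NEC sample positive. Nothing here shows that a positive result would be wholly due to NEC. The rule should be corrected before the data are analysed: the change is cheap, and a choice made after seeing results would be hard to defend.

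**What to change.** Amend the re-entry rule in Sample Analysis so that an infant's samples from the date of NEC diagnosis onward are not used in the primary before/after-anemia comparison, whatever their antibiotic timing. Add the NEC diagnosis date to the data list. Report the same analysis with those samples included, because NEC may itself follow an anemia-related shift. A further sensitivity analysis may omit infants who ever develop NEC, since diversity may already fall before diagnosis.

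The cost is one sentence in the sample rules, one date per NEC case, and a few late samples or pairs. If NEC lies on the path from anemia-related dysbiosis, the primary estimate may be slightly conservative; the analysis with those samples included would show by how much the estimate changes.

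### Multiples are eligible, but neither the 194 nor the named tests allow for sibling correlation, so the error rate and power may be misstated

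*Protocol*

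**What the plan says.** Protocol, Inclusion Criteria, opens eligibility to "Preterm infants less than 32 weeks gestation at birth", subject to age and feeding conditions. Nothing under Exclusion Criteria concerns multiple birth. Informed Consent describes screening and approach infant by infant, so two siblings can both be enrolled. Data Collection lists "Singleton/Multiple" as an item but no field that links an infant to its siblings.

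Under Groups, each infant supplies one sample before and one after the onset of anemia and acts as its own control.

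Sample Size Calculation states "Group sample sizes of 194 achieve 80% power to detect an odds ratio of 1.500". Its other inputs are two measurements per infant, a simple covariance, rates of 0.5 against 0.4, and a 5% significance level.

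Statistical Analysis names chi-square or Fisher tests for categorical factors and Student's t or Mann-Whitney tests for continuous factors. It then says "Repeated measurements will use analysis of variance (ANOVA) to compare groups". No family or sibling term appears in either section.

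**The concern.** In their usual form, all the named tests take infants as mutually independent. Repeated-measures ANOVA allows for correlation between samples from one infant, but not between infants.

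Co-multiples are unlikely to be independent here. The Background names delivery mode, feed type, medication and hospital exposure as influences on the gut microbiota, and siblings tend to share these more closely than unrelated infants do. They also share gestational age and date of birth, so they pass through the same developmental weeks together and reach the 38-week limit on sampling at the same time.

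Differencing before and after samples removes whatever level two siblings have in common. It does not remove a change they have in common, and the primary outcome is a change. If the changes of two anemic siblings are positively correlated, the pair carries less information than two unrelated infants. An analysis that ignores this understates the standard error. At stake are the nominal 5% error rate and the 80% power.

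**Working it through.** **Inputs from the Protocol (Sample Size Calculation).** Proportions 0.5 and 0.4, 80% power, alpha 0.05 (sidedness not stated), two repeated measurements, simple covariance structure, 194 per group.

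**Step 1: reproduce the 194.** The usual two-proportion formula, two-sided and without continuity correction, with mean proportion 0.45:

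n = [1.960 × √(2 × 0.45 × 0.55) + 0.842 × √(0.5 × 0.5 + 0.4 × 0.6)]² / 0.1²
= [1.960 × 0.7036 + 0.842 × 0.7]² / 0.01 = 387.3, rounded up to 388 observations per group.

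With two measurements per infant and within-infant correlation ρ, infants per group = 388 × (1 + ρ)/2. At ρ = 0 this is 194, an exact match, with power 80.1%. A one-sided test would give 152.5, and a continuity correction 204. The stated figure therefore corresponds to a two-sided test, uncorrelated measurements and independent infants, with no allowance for siblings.

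**Step 2: design effect for twins on the same side of the contrast.** Let f be the share of analysed infants with an analysed co-twin, and r the correlation of the siblings' changes. Among N infants there are fN/2 pairs, and each adds 2rσ² to the variance of the sum:

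variance of the sum = Nσ² + (fN/2) × 2rσ² = Nσ²(1 + f × r), so DE = 1 + f × r.

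If the analysis ignores this, the actual two-sided error is 2 × [1 − Φ(1.96/√DE)]. Effective n is 194/DE per group, and the number needed is 194 × DE. Power at 194, under an analysis that does allow for siblings, follows from the Step 1 formula with 388/DE observations per group.

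**Step 3: numbers.** The Protocol gives neither f nor r; both are assumptions.

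| f | r | DE | Actual two-sided error | Effective n per group | Needed per group | Power at 194 |
|---|---|---|---|---|---|---|
| 0.2 | 0.2 | 1.04 | 5.5% | 186.5 | 202 | 78.5% |
| 0.2 | 0.5 | 1.10 | 6.2% | 176.4 | 214 | 76.2% |
| 0.3 | 0.5 | 1.15 | 6.8% | 168.7 | 224 | 74.3% |
| 0.4 | 0.6 | 1.24 | 7.8% | 156.5 | 241 | 71.1% |

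**Step 4: siblings in opposite groups.** In a between-group comparison, a positive sibling correlation across groups reduces the variance of the difference: DE = 1 − f × r. With f = 0.3 and r = 0.5, DE = 0.85 and the actual error is 2 × [1 − Φ(1.96/√0.85)] ≈ 3.4%. The unadjusted test is then conservative.

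**The case against.** Several points weigh on the other side.

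- **A SAP may deal with it.** Only the Protocol is at hand, and a family term is ordinary SAP content. A reader might infer that the plan has decided to analyse siblings as independent; the Protocol nowhere says so. What stands is narrower: the Protocol itself fixes the tests and the sample size, both presuppose independent infants, and its data list has no sibling link from which a later adjustment could be built.
- **Infants are their own controls.** This is correct and important. A shared level cancels, and only correlation in the change matters. That correlation may be modest, because onset of anemia is specific to each infant and the before and after windows of two siblings need not coincide.
- **Few pairs may count.** A pair affects the primary contrast only if both siblings become anemic and both supply usable samples outside the antibiotic-related exclusions. The share that matters may therefore be well below the share of multiples enrolled.
- **The direction is not fixed.** A reader might infer that standard errors are always too small and that the type I error must exceed 5%. Step 4 shows otherwise for split pairs. In the stated paired design, two siblings who both become anemic do enter on the same side, so a positive correlation of their changes makes the unadjusted analysis optimistic there.
- **The power base is itself doubtful.** The 194 sizes two groups with uncorrelated repeat measurements, although the design is paired. Under the same formula, a within-infant correlation of 0.3 or 0.5 would cut power to 69% or 63%. That is a separate and larger problem. It means the power figures above show the sibling effect within the plan's own formula, not the true power of the paired design.

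These points limit the size and certainty of the concern but do not remove it.

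**Conclusion.** The concern holds in conditional form and is minor. That multiples can enter, that no rule limits families to one infant, and that the 194 and the named tests assume independent infants can all be read from the Protocol or reproduced from its figures. How far, and in which direction, this moves the error rate depends on quantities the Protocol does not give.

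The low end of the assumed range is close to negligible; only the top corner is substantial. The range rests on twins only, both siblings analysed, and both on the same side of the contrast. The documents do not support a claim that the error rate is in fact inflated, nor any single figure for it.

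**What to change.** - In Data Collection, add a family identifier beside singleton/multiple status.
- In Statistical Analysis, state that standard errors will be clustered on family, or that the model will carry a family-level random effect above infant. Either corrects the error in both directions.
- If diversity or composition is tested by permutation, permute whole families.
- In Sample Size Calculation, note that the 194 assumes independent infants, or give a design effect with its assumed inputs.

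The cost is one data field and one model term. The price in precision is usually slightly wider intervals.
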